7.0 PATHOLOGY

Does not apply to this study.

8.0 PATIENT ASSESSMENTS

8.1 Patient assessment will include the following:

8.1.1 Study Parameters.

	Pre-Treatment	During Treatment	Each Follow-up
History and Physical (including neurological assessments)	x	x	x
Karnofsky Status	x	a	x
Neurological Functional Classification	x	x	x
CT Scan	x		b
CBC, platelets	x	a	b
Urinalysis	x		
BUN, creatinine, uric acid	x	a	b
Alkaline Phosphatase, LDH, SGOT, bilirubin	x	a	b
Electrolytes	x	a	
Total Protein, Albumin	a	a	
Misonidazole Serum level		a	

- a) If receiving misonidazole (see Appendix V for additional assessments).
- b) If indicated.

0015936

- 8.1.2 Misonidazole Toxicity: The frequency, duration and grade of nausea and vomiting occurring in the patient will be recorded and evaluated.
- 8.1.3 The incidence and degree of peripheral and central neurologic toxicity and ototoxicity will be recorded and evaluated as a function of the number of drug administration, total drug dose, and plasma levels.
- 8.1.4 Mean plasma (4-6 hour) blood levels will be recorded for each drug administration and correlated with the observed frequency and severity of gastrointestinal and neurologic toxicity as well as the drug dose administered in terms of mg/m^2 and mg/kg .
- 8.1.5 Reactions to radiotherapy, both acute and late, will be recorded and included in the complete toxicity evaluation (Appendix IV). Toxicity occurring in any organ will be recorded, as will the location of the organ (within or outside of the radiation treatment volume).
- 8.1.6 Late normal tissue reactions should be recorded at the time of each follow-up according to the scale in Appendix VII.

8.2 Criteria for Tumor Response.

- 8.2.1 All neurological exams and CT scans are graded by comparing the results of the current test with the most recent preceding test. The scale below is to be followed:
- | | | | |
|----|-------------------------------------|----|-----------------------|
| -3 | Marked Deterioration | +3 | Marked Improvement |
| -2 | Definite Deterioration | +2 | Definite Improvement |
| -1 | Suspected Deterioration | +1 | Suspected Improvement |
| 0 | No change since previous evaluation | | |

- 8.2.2 Response is defined as definite (+2) improvement in at least one of these two parameters: neurological examination and CT scan, provided that the patient is on a stable or decreasing dose of steroids. A concomitant increase in steroid dose will rule out a "response" designation at this point. Suspected (+1) improvement will not designate response.

8.2.3 Conversely, progression is defined as definite (-2) deterioration in at least one of these two parameters: neurological exam and CT scan, provided that the patient has not had his/her dose of steroids decreased since the last course of therapy. A concomitant decrease in steroid dose will rule out a "progression" evaluation at that point. Suspected (-1) deterioration will not designate progression.

8.2.4 Stabilized disease (no change) is defined as stability or suspected (+1 or -1) changes in the test parameters, or improvement in one of the parameters, and deterioration in one parameter.

8.2.5 Follow-up assessments are to be done midway through treatment, upon completion of radiotherapy, then every three months until death. Patients receiving misonidazole are to have assessments done prior to each treatment according to misonidazole study parameters (Appendix VI). Every attempt should be made to obtain an autopsy for confirmation of tumor types and for studying radiation-sensitizer effects on normal brain.

8.3 Measurement of Specific End Points.

8.3.1 Relapse free interval will be measured from the first day of treatment until deterioration is documented as defined in 8.2.

8.3.2 Overall survival will be measured from the first day of radiotherapy until death.

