1.2 Misonidazole Background

Hypoxic cells are known to be present in solid tumors in man and animals, and are known to be more resistant to the effects of ionizing radiation than aerated cells. Whether or not the radioresistance of such cells is a limiting factor in the local control of solid tumors treated with radiotherapy is the subject of the current study. Attempts to improve the killing of hypoxic cells have involved the use of hyperbaric oxygen, high-linear-energy-transfer irradiation and hypoxic cell sensitizers. Of the compounds tested to date as hypoxic cell sensitizers, the nitroimidazoles appear to have the greatest potential because of their superior pharmacologic properties and greater effectiveness in mammalian cells. Among these, metronidazole (Flagyl) and misonidazole (Ro-07-0582) have proven to be active in animal model systems and are now in early clinical evaluation in several countries (1). Initial clinical pharmacologic and toxicologic evaluation of misonidazole by Dische et al. in England (2), by Urtusan et al. in Canada (3), and by Wasserman et al. in the United States (4) provides some qualitative and quantitative data on these drug properties for single dose and some multiple dose schedules. Pharmacologic studies using ultraviolet spectrophotometric (UV) and high-pressure liquid

0015922

chromatographic (HPLC) assays have established that peak serum levels of misonidazole occur 1-4 hours after the given dose with serum half lives ranging between 9 and 17 hours. Peak serum levels in mg/ml were slightly higher than drug dose administration in mg/kg. A good percentage of serum levels has been detectable in tumor biopsies and in the cerebrospinal fluid (CSF). Acute toxicity of the oral formulation has been expressed by nausea and vomiting. Multiple-dose schedules revealed the dose-limiting toxicity to be peripheral neuropathy, with the incidence apparently related to total drug dose given, dose frequency, and size of each individual drug dose.

The RTOG has completed a Phase I evaluation of misonidazole administered once and twice per week for 3 and 6 weeks and administered three times per week for 2 weeks and daily for 5 and 7 days. A total of 104 patients have been entered into this study. The results on the first 40 patients were presented to the American Society of Therapeutic Radiologists, November 1978, and the publication is in press (5).

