continued in the protocol as above. If the patient is withdrawn from misonidazole administration because of the above, call [name], Associate Chairman, [contact], or the sensitizer Co-Chairman for toxicity, [name]. His number is [contact]. If they cannot be reached inform [name], at [contact].

- 6.2.6 Details of drug administration. The drug shall be given at a dose of 2.5 g/m^2 once per week 4-6 hours before the neutron treatment for a total of 6 doses. Drug shall be given after a light meal. A compazine suppository of 25 mg shall be inserted 2 hours before drug administration unless the patient has a known allergy or reactivity to compazine. The total dose of drug administered under this protocol should not exceed 15 g/m^2 .
- 6.2.7 The number of radiation fractions and the number of misonidazole doses required by this protocol must be administered unless unacceptable toxicity as listed previously is encountered. Additional misonidazole will not be given beyond that specified by the protocol. Patients not responding well should not be removed from the study prior to administration of the prescribed radiation and misonidazole dosage unless unacceptable toxicity is encountered, or the patient refuses.
- 6.2.8 A minimum of two blood levels are required. Initial blood levels should be obtained 4-6 hours after the drug administration (at the time of radiation) and a second blood level should be obtained 24-28 hours after drug administration. If the 4-6 hour blood level varies from the mean by more than two standard deviations per the table below, then a repeat of the measurement after the next dose of Misonidazole must be made. If the 24-28 hour concentration is greater than 25% of the 4-6 hour concentration, then a repeat of both measurements with the next dose of Misonidazole must be made. If the repeat measurements confirm the initial variation of either the 4-6

0015935

hour or the 24-28 hour concentrations, then the Cochairman for sensitizers should be called for the appropriate dose reduction of Misonidazole.

Relationship of Dose to Mean 4-6 Hour Serum Level

Dose = 2.5 gm/m²

	Phase I	Phase II
No. of Doses (Determinations)	43	324
Mean 4-6 Hr. Serum Level ug/ml	98	83
+/- Standard Deviation	23	29
Observed Range	35-148	4-165

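### The 25% ratio trigger in section 6.2.8 would flag most patients on the half-lives in section 1.2, and the level correlations in section 8.1.4 do not allow for the dose reductions that may follow

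*Protocol*

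**What the plan says.** Dose: section 6.2.6 gives everyone the same amount: "The drug shall be given at a dose of 2.5 g/m^2 once per week", six times.

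Sampling: section 6.2.8 requires at least two levels. "Initial blood levels should be obtained 4-6 hours after the drug administration", and "a second blood level should be obtained 24-28 hours after drug administration".

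Triggers: a repeat with the next dose is required if the 4-6 hour level lies more than two standard deviations from the tabulated mean. It is also required for both samples on this condition: "If the 24-28 hour concentration is greater than 25% of the 4-6 hour concentration". If the repeat confirms either finding, the co-chairman for sensitizers "should be called for the appropriate dose reduction of Misonidazole". The size of the reduction is not given.

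Half-lives: section 1.2 reports "serum half lives ranging between 9 and 17 hours".

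Analysis: under section 8.1.4, mean 4-6 hour levels "will be recorded for each drug administration and correlated with the observed frequency and severity of gastrointestinal and neurologic toxicity". The same sentence adds a second correlation, with dose in two units (mg/m² and mg/kg), through the words "as well as the drug dose administered in terms of". The section does not separate levels before a reduction from those after it. Footnote a of Appendix VI schedules the peak serum level after the first misonidazole dose only, which does not fit the wording of 8.1.4.

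**The concern.** Two things do not fit together.

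First, the ratio trigger is written as a screen for unusual patients. Its companion limit, two standard deviations on the 4-6 hour level, would be crossed by about 4.6% of single normally distributed readings. If the ratio limit sits below what the stated half-lives produce in an ordinary patient, the screen becomes the normal path. Most patients would then lead to a repeat and a call about reducing the drug, and the trial would no longer describe tolerance at 2.5 g/m².

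Second, section 8.1.4 relates level to dose and toxicity as if dose were fixed in advance. After the second administration it may depend on the patient's own measurements. The level-mg/m² correlation would then have little meaning, and a level-neuropathy correlation pooled over administrations would mix early unreduced levels with later lowered ones, although section 1.2 ties neuropathy partly to total drug given.

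**Working it through.** The protocol gives no figure for the share of patients reaching the rule, so there is none to reproduce.

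**1. Sampling gap (6.2.8).** Shortest 24 − 6 = 18 h, longest 28 − 4 = 24 h, midpoints 26 − 5 = 21 h.

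**2. Half-life at which the trigger fires.** Assuming mono-exponential decay between samples, ratio = 2^(−gap/half-life). This exceeds 0.25 when half-life > gap/2, that is 9 h, 10.5 h or 12 h for gaps of 18, 21 or 24 h.

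**3. Ratios over the range in 1.2.**

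| Half-life | 18 h gap | 21 h gap | 24 h gap |
|---|---|---|---|
| 9 h | 25% | 20% | 16% |
| 13 h (midpoint) | 38% | 33% | 28% |
| 17 h | 48% | 42% | 38% |

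The midpoint patient exceeds 25% at every permitted gap.

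**4. Share flagged.** The protocol gives no distribution. If half-lives are uniform over 9-17 h:
- 18 h gap: (17 − 9)/8 = 100%
- 21 h gap: (17 − 10.5)/8 = 81%
- 24 h gap: (17 − 12)/8 = 63%

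Normal distributions tried instead gave 60% to 98%. Requiring confirmation at the second dose leaves about 75%, or roughly 19 of the 25 patients planned in section 10.2.

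**5. The level trigger.** Its limits are 98 ± 2 × 23 = 52 to 144 µg/ml (Phase I column) or 83 ± 2 × 29 = 25 to 141 µg/ml (Phase II column). A confirmed high level occurred in about 1% of simulated patients or fewer. Nearly all flags come from the ratio, which reflects elimination rather than the 4-6 hour level itself.

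**6. Level against mg/m².** Section 6.2.8 is the only written rule that lowers an individual patient's dose. Section 6.2.5 stops the drug for neurologic toxicity or ototoxicity and bars reduction for nausea or vomiting; section 10.2 allows for trial-wide modification but gives no rule. Without reductions, mg/m² per administration is constant apart from rounding to capsules, and the correlation is undefined. With them, the yardstick is the slope 98/2.5 ≈ 39 µg/ml per g/m².

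A simulation assumed uniform half-lives, a mean level of 98 µg/ml, between-patient spread of 15-25%, within-patient spread of 15%, and reductions from dose 3. Giving the same reductions at random recovered slopes of 39 to 40. Under the rule:

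| Reduction (assumed) | 10% | 20% | 33% | 50% |
|---|---|---|---|---|
| Slope per administration | 22 | 31 | 35 | 37 |
| Correlation per administration | 0.11 | 0.32 | 0.55 | 0.75 |
| Slope per patient | −14 | 14 | 24 | 30 |

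The correlation is set largely by how big the reductions are.

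**7. Level against neuropathy, patient means, same simulation and same order of reductions.**
- Toxicity follows total exposure: 0.46, 0.43, 0.41, 0.38, against 0.48 with no reductions and 0.49 to 0.55 with random ones.
- Toxicity follows the 4-6 hour level: 0.51 to 0.54, against 0.51 with none and 0.52 to 0.59 with random ones.

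**8. Level against neuropathy, pooled over administrations.** A simulation of 25 patients and six doses assumed neuropathy driven by cumulative level times half-life, level and half-life correlated 0.2-0.5, and the drug stopped at Grade 2. The correlation fell from 0.17-0.29 without reductions to between −0.02 and 0.18 with 20-30% reductions.

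**The case against.** The strongest counter-arguments, and what stands of each:

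- **Flagging is not reduction.** The text requires a confirming repeat and then a call, with no stated size. A reader might infer that most patients will have their dose lowered; the document supports only that most would reach the call. This stands as a limit. The conflict between the limit and the half-lives does not depend on it.
- **The frequent trigger is not the level in 8.1.4.** A reader might infer that dose is a consequence of the 4-6 hour level, so that level and mg/m² run in opposite directions. That would follow from the high-level trigger, which hardly ever fires. Across the settings tried, the per-administration correlation was about 0 to 0.81. The one negative slope in the table is per patient at a 10% reduction.
- **The toxicity effect may be small.** A reader might infer that the level-neuropathy relation would be reversed. The simulations do not show that: the usual result is attenuation, sometimes slight, and the lowest pooled value is essentially zero. With 25 patients the standard error of a correlation is about 1/√25 = 0.2, larger than the loss seen with patient means.
- **8.1.4 fixes no unit of analysis.** Pooling over administrations is one reading, and an analysis plan could choose another. Section 8.1.3 also evaluates neurotoxicity by number of administrations and total dose. Under the Appendix VI schedule nearly all levels would precede any reduction, and the mechanism would largely vanish. This stands, and it is why that schedule must be reconciled with 8.1.4.
- **An early level is not uniformly better.** Replacing all levels by a pre-reduction mean loses to the ordinary patient mean when toxicity follows the level, and it discards the dose-by-dose pairing that suits nausea. This stands and shapes the fix.

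**Conclusion.** The point holds, and its main part is the conflict between sections 6.2.8 and 1.2. On the protocol's own sampling times and half-lives, the 25% limit is exceeded by the patient in the middle of the stated range. It would flag 63% to 100% if half-lives are uniform, and about 75% after confirmation. This rests on mono-exponential decay and on a distribution that the document does not give; half-lives bunched near 9 hours would lower the share.

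The correlation wording in 8.1.4 is a minor matter. The mg/m² correlation is uninformative as written: undefined without reductions, and otherwise a reflection of reductions chosen from patients' own measurements. The level-neuropathy correlation can be attenuated if administrations are pooled. By how much depends on the unstated reduction size and on what drives toxicity.

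**What to change.** 1. Reconcile the 25% trigger in 6.2.8 with the half-lives in 1.2. No threshold is proposed here; that is for the investigators.
2. Reconcile 8.1.4 with Appendix VI on which doses have a level taken.
3. In 8.1.4, replace the mg/m² correlation with the mean and SD of levels at the unreduced 2.5 g/m², and run the mg/kg correlation on unreduced doses only.
4. Flag every level taken after a level-driven reduction. Report the neurotoxicity correlation per patient, with pre-reduction levels shown separately beside the all-dose mean.
5. Keep the administration-by-administration pairing for nausea and vomiting.

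Items 3 to 5 change analysis wording only and need no extra blood samples. They add a little analysis, and they reduce the bias without removing it, because toxicity in a patient whose dose was lowered still reflects the lower later exposure.

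### Section 8.2 scores progression only against the preceding test, gives two conflicting steroid windows and lets discordant results fit three categories, which distorts the relapse-free interval

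*Protocol*

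**What the plan says.** All of this is in section 8.0 of the protocol.

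- **Reference (8.2.1).** "All neurological exams and CT scans are graded by comparing the results of the current test with the most recent preceding test". The scale runs from -3 to +3; 2 is a definite change and 1 a suspected change.
- **Response (8.2.2).** A definite improvement in the neurological exam or the CT, on a stable or falling steroid dose.
- **Progression (8.2.3).** A definite deterioration in either parameter, "provided that the patient has not had his/her dose of steroids decreased since the last course of therapy". The next sentence reads: "A concomitant decrease in steroid dose will rule out a 'progression' evaluation at that point". The paragraph ends: "Suspected (-1) deterioration will not designate progression".
- **Stable disease (8.2.4).** "Stabilized disease (no change) is defined as stability or suspected (+1 or -1) changes in the test parameters". The same category also takes in the discordant case, where one measure gets better while the other gets worse.
- **Schedule (8.1.1, 8.2.5).** Assessments fall before each misonidazole treatment, midway through and at the end of radiotherapy, "then every three months until death". The table in 8.1.1 lists neurological assessment at all stages. It lists CT before treatment and, at follow-up, only when indicated.
- **Endpoint (8.3.1).** "Relapse free interval will be measured from the first day of treatment until deterioration is documented as defined in 8.2".

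Section 10.2 bases acceptance of the treatment on local control at one year, and the protocol does not define that term.

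**The concern.** A progression rule should give the same answer for the same deterioration, whatever the number of visits over which it occurs. This one does not, because its reference moves at every visit and no provision looks back to entry or to the best status reached. The more often a patient is examined, the smaller each step is likely to be, and the easier it is for a real decline to stay below a definite change. The neurological exam is the parameter most exposed, since it is repeated far more often than CT.

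The steroid exclusion adds a second way to lose an event, and the overlap of 8.2.2 to 8.2.4 leaves some patients with no unique category. Section 8.3.1 ends the relapse-free interval only at deterioration as 8.2 defines it, so each fault passes straight into that endpoint. Objective 2.3 asks whether disease-free interval and local control lie within the expected ranges. That comparison needs a failure date that does not depend on how the decline was divided among visits.

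**Working it through.** **1. Patient courses put through the rules as written.** The courses are hypothetical. Steroids are steady unless noted.

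| Course (grade against the test before) | Result under 8.2 | Relapse-free interval |
|---|---|---|
| Neurological exam -1, -1, -1, -1 at four three-monthly visits | Stable at each visit | Still running after a year of decline |
| +2, then -2 (back to about entry status) | Response, then progression | Ends |
| +2, then -1, -1 (a similar loss in two steps) | Response, then stable | Still running |
| -2 during a taper, then 0 | First visit excluded; second stable | Still running; event never recorded |
| CT +2 and neurological exam -2 at one visit | Response, progression and stable | Undetermined |

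The second and third courses lose a similar amount of function, yet only one counts as a relapse.

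**2. The two steroid windows in 8.2.3.** The proviso excludes progression after any decrease since the last course of therapy. The protocol has one treatment course. If that is the course meant, a post-treatment taper could exclude progression at every later visit. The following sentence limits the exclusion to a concomitant decrease at the visit in question. Even then the event can be lost, as in the fourth course, because 8.2.1 makes the worsened test the new reference. Nothing in 8.2 requires a repeat assessment or back-dating. An excluded -2 with no change in the other parameter also fails the 8.2.4 definition, so that visit has no category.

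**3. The plan's own figures (10.2, 25 patients).**

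- Seeing a one-in-ten complication: 1 - 0.9^25 = 0.928, which agrees with the stated 93%.
- Acceptance: over 90% at true control of 45%, under 25% at 25%. No cut-off is printed. With at least 8 of 25 controlled, the uncorrected normal approximation gives 90.4% and 20.9%, which agrees. Exact binomial gives 93.6% and 27.3%. With at least 9 of 25, exact binomial gives 86.6% and 14.9%.

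**4. An outer limit for local control, on assumptions.** Suppose that 8.2 determines local control, that a patient dead at one year is a failure, that every controlled patient is alive, and that the 27-39% twelve-month survival in section 1.1 applies here. At true control of 25%:

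- living failures are 27 - 25 = 2% to 39 - 25 = 14% of all patients;
- as a share of failures this is 2/75 = 2.7% to 14/75 = 18.7%;
- if every one of them were missed, apparent control would be 27% to 39%.

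| Assumed cut-off | None missed (25%) | All living failures missed (27% to 39%) |
|---|---|---|
| At least 8 of 25 | 27.3% | 35.7% to 82.1% |
| At least 9 of 25 | 14.9% | 21.2% to 69.1% |

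Entries are exact binomial chances of acceptance. The last column is a ceiling for undetected failures and not an estimate, because some living failures will show a definite step and be scored.

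**The case against.** Several counter-arguments carry weight.

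- **A -1 is a grade of certainty.** It means suspected change and cannot be summed across visits. That is right, and the point does not sum grades. It is that a change only suspected from one visit to the next may be definite against entry, and 8.2 never makes that comparison.
- **CT is less exposed.** With no CT listed during treatment and follow-up CT only when indicated, the first follow-up scan will normally be compared with the post-surgical one. This stands, and confines the gradual-decline problem mainly to the neurological exam.
- **Section 8.2.4 may be meant as the rule for discordant results.** That is a fair reading, but 8.2.2 and 8.2.3 each need only one parameter and make no exception for it.

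A reader might go further in four ways that the documents do not support.

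- *That the bias always favors the treatment.* A responder who slips back in one step is scored as progression. A -2 on the neurological exam also counts whatever its cause, including misonidazole or radiation injury. Slow improvement in +1 steps is never a response.
- *That 8.2 is the only basis for local control.* Appendix VI also records local disease status and lesion size at entry, at each dose and at follow-up, and the codes printed with Appendix IV include progression. That code also looks back to the last measurement, so it does not cure the problem, but the link from 8.2 to 10.2 remains an inference.
- *That a taper does bar progression for good.* This is one of two readings of 8.2.3.
- *That a particular inflation of the acceptance chance is established.* Missing 20% of failures would exceed the 18.7% ceiling above. No miss rate or cut-off is in the documents, and with a cut-off of 8 the exact 27.3% exceeds the stated limit before any misclassification.

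**Conclusion.** The point holds on the wording of 8.2 alone, for three faults: a moving reference with no look-back, two irreconcilable steroid windows with no re-evaluation, and overlapping categories with no precedence. Through 8.3.1 they distort the relapse-free interval directly. Overall survival, which runs to death under 8.3.2, is unaffected. An effect on one-year local control is likely but rests on the inference that 8.2 would define it. Its size cannot be derived, and the range shown depends on the assumed cut-offs, on deaths counting as failures and on the survival figures in section 1.1. A steroid condition on response and progression is reasonable in itself; the faults are its unclear window and the missing re-assessment. The rules should be changed before the endpoints are scored.

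**What to change.** 1. Grade response against the pre-treatment exam and post-surgical CT, and progression against the best status since entry. Keep the visit-to-visit grade as a record. Under this rule a responder who definitely loses the gain is a progression whether the loss takes one visit or several. If the sponsor wants relapse to mean worse than entry, the protocol should say so and use the entry status as the reference.
2. Reconcile the two steroid sentences in 8.2.3 to one window: a decrease since the comparison test. When it applies, re-evaluate at the next visit against the same reference and, if deterioration is confirmed, date progression to its first appearance. This concerns scoring only and changes no steroid management.
3. State one rule for improvement in one parameter with deterioration in the other, and word 8.2.2 to 8.2.4 so that every visit falls into exactly one category.

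The cost is protocol wording and some re-scoring. Re-scoring is possible only where serial exams and scans exist: follow-up CT is not mandatory, and section 9.5 asks for exam copies only in Grade III or IV neuropathy. The reported relapse-free interval may become shorter. Treatment does not change.

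### Tumour status is graded only against the preceding test, so a decline made up of suspected steps is never progression and some rebounds count as response

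*Protocol*

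**What the plan says.** Section 8.2.1 of the protocol sets the reference for every grade: "All neurological exams and CT scans are graded by comparing the results of the current test with the most recent preceding test". The scale runs from -3 to +3, and its zero point is "No change since previous evaluation".

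The categories are built on that step change:

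- **Response (8.2.2):** "Response is defined as definite (+2) improvement in at least one of these two parameters: neurological examination and CT scan", on a stable or decreasing steroid dose. A +1 step does not count.
- **Progression (8.2.3):** "progression is defined as definite (-2) deterioration in at least one of these two parameters: neurological exam and CT scan", unless steroids were decreased. The section adds: "Suspected (-1) deterioration will not designate progression".
- **Stabilized disease (8.2.4):** "Stabilized disease (no change) is defined as stability or suspected (+1 or -1) changes in the test parameters".

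Assessments fall midway through treatment, at the end of radiotherapy and every three months after that (8.2.5). In addition, "Patients receiving misonidazole are to have assessments done prior to each treatment". Follow-up CT is done only if indicated (8.1.1). Section 8.3.1 takes its event from this grading: "Relapse free interval will be measured from the first day of treatment until deterioration is documented as defined in 8.2".

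**The concern.** The reference moves with the patient. Each visit resets the comparison, so the rule measures change between neighbouring visits and never distance from the pretreatment state. Two errors can follow. Gradual worsening can go unrecorded as progression, which lengthens the relapse free interval. Recovery from a temporary dip can be recorded as tumour response although the patient is no better than at the start.

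Objective 2.3 asks whether tumor clearance, disease-free interval and local control lie in the expected range. The study is also meant to lay the basis for a Phase III trial (2.1). An endpoint that misses slow decline, or counts a return to baseline as benefit, weakens that reading.

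**Working it through.** **1. The rule applied to example courses.** The documents give no figure to reproduce, so 8.2.1 to 8.2.4 are applied as written and then with a fixed reference (response against pretreatment, progression against best prior status, same thresholds and steroid conditions). Adding grades is a simplification, because the scale is ordinal.

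| Successive grades | As written | Fixed reference |
|---|---|---|
| -1 five times | Stabilized five times, no progression | Progression at the second step |
| -1, -1, +2 (back to start) | No progression, then response | Progression at the second step, no response |
| -2 during a steroid decrease, then +2 on stable steroids | No progression, then response | Neither |
| -2 on stable steroids, then +2 | Progression, then response | Progression, no response |

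**2. Does another section repair this?** None adds up steps, requires confirmation, or refers response or progression to pretreatment or best status. Appendix VI records lesion size and local disease status, and the pretreatment CT is mandatory (4.2.1), but 8.2 gives none of them a role as a fixed reference. The disease-status code for progression printed with the toxicity criteria is also relative to the last measurement.

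**3. How large could the effect be?** This step rests on assumptions. Take a straight-line decline in units of one definite step and call progression at a fall of 1 unit or more. Tests are at weeks 0, 1, 2, 3, 4, 5, 5.2, 18, 31, 44 and 52, with normal noise on each test and 20,000 draws. The longest gap is 13 weeks, so without noise the written rule can act only at 52/13 = 4 steps per year or more. At 3 steps per year the largest single fall is 3 × 13/52 = 0.75. Four such falls total 4 × 0.75 = 3 units and are never progression. Against pretreatment, the second such fall already gives 2 × 0.75 = 1.5.

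Proportion called progression within a year (noise SD 0.1 to 0.2):

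| True loss per year | As written, exam only | As written, plus one CT at week 31 | Exam against pretreatment |
|---|---|---|---|
| 2 steps | 0–12% | 78–91% | 100% |
| 3 steps | 11–53% | about 100% | 100% |
| 4 steps | 95–96% | – | – |

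The CT column matters because no CT is scheduled during treatment. The first follow-up CT is therefore normally compared with the pretreatment scan: at week 31 and 2 steps per year the fall is 2 × 31/52 = 1.19. With CTs at weeks 18 and 44, detection is 51–66% at 2 steps and about 100% at 3.

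**4. Cost of a best-status reference.** With no true decline, noise SD up to 0.2 gives false progression in under 1%. At SD 0.3 it is 26%, against 9% as written. At SD 0.4 it is 65%, against 34%.

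**5. If 8.2 also decided local control (not stated).** Let m be the share of failures missed at a true control rate of 25%, so apparent control is q = 0.25 + 0.75m. The protocol gives no acceptance cut-off; assume 8 or more of 25. P(X ≥ 8) is 0.27 at m = 0, 0.43 at m = 5% (q = 0.2875), 0.60 at m = 10% (q = 0.325) and 0.85 at m = 20% (q = 0.40).

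**The case against.** The strongest reply is that the gap is real but its effect may be modest. Progression needs a definite fall on the exam or on CT, and the first follow-up CT usually supplies the pretreatment comparison. Section 1.1 gives survival of 27–39% at 12 months and describes relentless local growth, so slow linear decline over a whole year is not shown to be typical. At 4 steps per year the written rule finds nearly all cases. The grades mix certainty with extent, so steps per year is a modelling device. All of this stands, and it is why the percentages above cannot be read as the trial's expected error.

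A reader might infer more, in three ways that the documents do not support:

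- **That the rule always favours the regimen.** The acceptance statement in 10.2 concerns local control, so inflated response does not enter it. A single -2 dip without a steroid decrease is scored as progression first, and a transient dip can therefore shorten the relapse free interval.
- **That one-year local control must rest on 8.2.** The protocol does not link them, and local disease status is recorded separately in Appendix VI.
- **That drug neuropathy would generally produce false responses.** Neuropathy has its own toxicity scales (6.2.3.2). The routes that escape progression are narrow: a dip in -1 steps or during a steroid decrease, then a +2 recovery on stable or decreasing steroids.

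Section 8.3.1 says deterioration rather than progression. Reading that to include -1 would soften the point for relapse free interval only, and it fits poorly with 8.2.3.

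**Conclusion.** The point holds as a defect in the stated endpoint definition, and the first two steps of the check show it by logic alone. A decline graded suspected at every visit is never progression, and two kinds of rebound count as response with no net gain. A -2 dip without a steroid decrease is caught as progression, though the later +2 still meets 8.2.2.

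The likely effects are a longer relapse free interval for gradual decline and an overstated response rate. An effect on one-year local control is possible only if 8.2 decides it. The size is not computable from the documents: the simulated figures rest on assumed rates of decline, noise and CT timing, and they range from almost no detection to almost complete detection. Toxicity assessment and overall survival are untouched. In a 25-patient, non-randomized Phase I/II study this should be fixed, but it does not undermine the trial as a whole.

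**What to change.** In 8.2.1 to 8.2.3:

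- Grade response against the pretreatment (post-surgical) exam and CT.
- Grade progression against pretreatment or the best status recorded since then.
- Leave the thresholds and steroid conditions as they are.
- Where best status is the reference, require that a borderline progression seen on the exam alone be borne out at the next scheduled assessment.
- Keep the change from the preceding test as a descriptive item.

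The cost is a few sentences and one extra grade on the form. The pretreatment exam (4.1.1) and post-surgical CT (4.2.1) are already mandatory. There are two downsides: assessors must look back past the last visit, and a best-status reference raises false progression when grading is noisy, which is the reason for the confirmation step.
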